## 9B. Specific Aims of Combination therapy pilot study

# Specific Aim 1 will test the hypothesis that a 2 to 6 week course of anakinra and atorvastatin in combination will be safe and well-tolerated in children with acute KD who have a Z-score of $\geq$ 2.5 of LAD or RCA.

While the safety of anakinra will be assessed by monitoring for leukopenia, infection and injection site reactions, the safety of atorvastatin will be assessed by monitoring for liver and muscle toxicity as well as total and 24-OH cholesterol levels.

# Specific Aim 2 will test the hypothesis that a combination of anakinra and atorvastatin therapy will decrease systemic inflammation and restore endothelial cell dysfunction.

Cytokine levels and matrix metalloproteinase activity in sera and transcript abundance in whole blood RNA will be measured pre- and post-treatment. These sera will also be tested *in vitro* with cultured endothelial cells with read-outs for innate immune signaling pathways and endothelial to mesenchymal transition (EndoMT).

# **10.Timeline**

Table 3. Timeline of studies								
Study and Task	2015	2016	2017	2018	2019	2020	2021	2022
Phase I/IIa anakinra study								
Spec Aim1: Safety/ tolerability/dose escalation								
Spec Aim 2: PK & Anti- inflammatory Studies								
Data analysis and manuscript     preparation								
Combination therapy pilot study								
IND amendment and IRB     approval								
Spec Aim 1: Safety/tolerability								
Spec Aim 2: Anti-inflammatory studies								
Data analysis and manuscript     preparation								

# 11. Study design

#### 11A. Accrual and Study Duration

#### 11A1. Accrual and study duration for Phase I/IIa anakinra study

We estimate enrolling 0-2 patients per month at the two research sites over the course of a year with a target enrollment of 30 patients over a 4 year period. All subjects enrolled will be in the study for up to 6 weeks during which time they will receive once or twice daily subcutaneous injections of anakinra administered by the parents at home.

#### 11A2. Accrual and study duration for Combination therapy pilot study

We estimate enrolling 0-2 patients every 6 months with a target enrollment of 10 patients over a 5year period. All subjects enrolled will be in the study for up to 6 weeks during which time they will receive once or twice daily subcutaneous injections of anakinra and once daily oral administration of atorvastatin administered by the parents at home.

### 11B. Inclusion

#### 11B1. Inclusion for Phase I/IIa anakinra study

- Meets clinical criteria for KD according to American Heart Association guidelines (Table 4): Fever (T≥38°C or 100.4°C) ≥ 3 days and ≥ 2 clinical criteria with LAD or RCA z-score ≥ 2.5
- 2. Patient is at least 28 days old
- 3. Patient presents within the first 20 days after fever onset
- 4. Parent or legal guardian able and willing to provide informed consent
- 5. Able to be dosed between 20 mg (min amount on syringe) and 200 mg at 8 mg/kg/day

Dose escalation level*	Minimum subject weight to administer 20 mg	Maximum subject weight to administer 200 mg
8 mg/kg	2.5 kg	25 kg

\*This table includes only the 8 mg/kg dose level as enrollment in the 4 and 6 mg/kg cohorts has been completed as of the Nov 2016 revision.

\*As of the August 2017 revision, we have enrolled 2 subjects at 8mg/kg/day without any dose limiting toxicities.

#### 11B2. Inclusion for Combination therapy pilot study

- 1. Meets clinical criteria for KD according to American Heart Association guidelines (**Table 4**): Fever (T≥38°C or 100.4°C) ≥ 3 days and ≥ 2 clinical criteria with LAD or RCA z-score ≥ 2.5
- Patient at least 2yo and weighs ≤ 25 kg (weight limit based on anakinra max dose of 200 mg/day at a calculated dose of 8 mg/kg/day)
- 3. Patient presents within the first 20 days after fever onset
- 4. Parent or legal guardian able and willing to provide informed consent

# Table 4. Diagnostic criteria for KD with CAA (Adapted from American Heart Association (Newburger 2004)):

KD standard clinical criteria :

- Bilateral conjunctival injection
- Changes of the mucous membranes of the upper respiratory tract: injected pharynx, injected, fissured lips, strawberry tongue
- Changes of the peripheral extremities: peripheral edema, peripheral erythema, periungual desquamation
- Polymorphous rash
- Cervical adenopathy >1.5 cm

#### 11C. Exclusion

#### 11C1. Exclusion for Phase I/IIa anakinra study

- 1. Use of an IL-1beta antagonist within the 3 months prior to enrollment
- 2. Have any chronic disease, except asthma, atopic dermatitis, autism or controlled seizure disorder
- 3. Patient has a history of hypersensitivity to anakinra
- 4. Personal or immediate family history of tuberculosis (TB) or TB exposure
- 5. Active, culture-positive bacterial infection
- Baseline Scr ≥ 0.50 mg/dL (28 days old to 1 year old) or an eGFR lower than 45 mL/min/1.73m^2 (≥ 1 year old)

#### 11C2. Exclusion for Combination therapy pilot study

- 1. Use of an IL-1beta antagonist within the 3 months prior to enrollment
- 2. Have any chronic disease, except asthma, atopic dermatitis, autism or controlled seizure disorder
- 3. History of hypersensitivity to anakinra
- 4. Personal or immediate family history of tuberculosis (TB) or TB exposure
- 5. Active, culture-positive bacterial infection
- 6. Baseline eGFR lower than 45 mL/min/1.73m^2 (as subjects  $\geq$  1 year old)
- 7. Use of a statin, fibrate, or niacin within the 3 months prior to enrollment
- 8. Screening creatine phosphokinase (CK)  $\geq$  3x upper limit of normal for age
- 9. Taking a CYP3A4 inhibitor (i.e. cyclosporine, clarithromycin or doxycycline) in the last 7 days
- 10. History of allergy to atorvastatin or its derivatives

## 11D. Data Collection

#### 11D1. Data collection for Phase I/lla anakinra study

#### 1. Demographic data:

- a. Patient's age at KD onset, sex, self-reported ethnicity of each biologic parent
- 2. Clinical data:
  - a. Physical findings confirming the KD case definition(Newburger 2004)
  - b. Illness day at study entry
  - c. Response to IVIG (IVIG-resistance will be defined as persistent or recrudescent fever (T≥38.0°C rectally) ≥36 h and < 7d following the end of the IVIG infusion (2g/kg) ([name] 2008).
  - d. Name, dose and indication of concomitant medications taken while on study
  - e. Complete white blood count (WBC), hsCRP, erythrocyte sedimentation (ESR), fibrinogen, and alpha-1-antitrypsin levels at baseline, 48 hours (not ESR as IVIG recently administered), 2 weeks and 6 weeks (if still on study drug) after drug administration
  - f. Serum creatinine at baseline prior to receiving study drug
  - g. Severity and duration of infections (with any associated cultures or diagnostic testing) during study
  - h. Echocardiographic data at baseline, 48 hours, and 2 and 6 weeks (standard of care for patients with CAA)

#### 11D2. Data collection for Combination therapy pilot study

#### 1. Demographic data:

a. Patient's age at KD onset, sex, self-reported ethnicity of each biologic parent

#### 2. Clinical data:

- a. Physical findings confirming the KD case definition (Newburger 2004)
- b. Illness day at study entry
- c. Response to IVIG (IVIG-resistance will be defined as persistent or recrudescent fever (T≥38.0°C rectally) ≥36 h and < 7d following the end of the IVIG infusion (2g/kg) ([name] 2008).
- d. Name, dose and indication of concomitant medications taken while on study
- e. Serum creatinine at baseline prior to receiving study drug
- f. Severity and duration of infections (with any associated cultures or diagnostic testing) during study
- g. Complete blood count, CRP, hsCRP, ESR, aspartate aminotransferase (AST), and ALT at baseline, 48 hours (not ESR as IVIG recently administered), and 2 and 6 weeks
- h. CK and fasting lipid panel at baseline (after enrollment), 48 hours, and 2 and 6 weeks (if still on study drug)
- i. Echocardiographic data at baseline, 48 hours, and 2 and 6 weeks (standard of care for patients with CAA)

#### 11E. Laboratory Samples

#### 11E1. Laboratory samples for Phase I/IIa anakinra study

Subjects will have the following samples collected at baseline (pre- anakinra), 48 hours and 2 and up to 6 weeks (if still on study drug) (+/- 7 days) from enrollment:

**1. RNA collection:** Whole blood RNA will be collected using PAX gene tubes. RNA will be isolated according to the manufacturer's instructions and aliquoted and stored at -80°C.

**2. Plasma, serum, and heparinized whole blood collection:** EDTA plasma and serum will be collected for measures of inflammation. Whole blood (5 ml in large green top) in a sodium heparin tube will be collected for T cell subset and cytokine studies.

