# Specific Aim 2 will describe the pharmacokinetics of anakinra and test the hypothesis that anakinra will decrease systemic and coronary artery inflammation associated with acute KD.

Blood will be tested pre-drug administration, 48 hours after initiation of therapy and at 2 weeks and 6 weeks for markers of inflammation and enumeration of dendritic cells and T cells. Echocardiographic assessment of CAA at these time points will be compared to historical controls matched for age, sex, illness day at diagnosis, and coronary artery status on initial echo.

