#### 12B. Duration of Study Drug

#### 12B1. Duration of study drug for Phase I/IIa anakinra study

All subjects will receive 2 weeks of therapy. Subjects with an echo at 2 weeks that shows either a LAD or RCA z-score  $\geq$  2.0 will receive an additional 4 weeks of therapy to complete a total course of 6 weeks. All subjects will remain on study for the full 6 weeks whether or not they are receiving anakinra.

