# 17. Immune Monitoring for Phase I/IIa anakinra study

PBMC will be separated by Ficoll Hypaque from KD subjects at three time points (pre-treatment, 2 weeks, and 6 weeks post-treatment) for staining with specific monoclonal antibodies (MoAbs) to characterize DC lineages, macrophages and their activation/maturation stage. Anti-DR (MHC class II molecules) and anti-CD86 define maturity and activation. CD11c defines the DC lineage, and is not expressed on macrophages. Antibodies anti-CD11c will be used in combination with anti-DR and anti-CD86 and other markers, well described in the literature. Briefly: to define myeloid DC: anti-CD11b, (also expressed on macrophages but negative in plasmacytoid DC and thymic DC) and anti-BDCA-1. To define immature tolerogenic myeloid DC very relevant in the immune-regulation in KD, we will look at CD14, co-expressed on macrophages but not on plasmacytoid DC, in CD11c + CD11b + myeloid DC. Macrophages will be identified by the expression of CD11b and CD14 in CD11c negative cells. To enumerate activated CD4+ and CD8+ T cells and regulatory T cells (Treg) we will use anti-

CD4, anti-CD8, anti-DR, anti-CD25 (Treg are CD25high) and anti-IL-7 receptor, expressed on proinflammatory cells and peripherally-induced Treg but not in natural Treg.

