#### 19B. Statistical analysis of inflammatory studies

**19B1. Statistical analysis of inflammation studies for Phase I/IIa anakinra study** The objective of this matched case-control study is to determine the activity profile of anakinra in the treatment of KD subjects with CAA. Measures of inflammation will be compared to that of matched controls via paired statistical tests (e.g. McNemar's test for categorical outcomes or the paired t-test for continuous outcomes). Non-parametric alternatives will be considered only if distributional assumptions are violated.

**Control Group:** Controls will be chosen from the >600 subjects with data in our web-based data repository in REDCap. Controls will be matched to study patients based on age, sex, Illness Day at diagnosis, and baseline Z score.

**Analysis:** Each marker will be initially summarized descriptively and analyzed individually. Separate multivariable mixed effects regression modeling for clustered data (to account for the case-control paired nature of samples) will be used to characterize the markers of anakinra-treated subjects versus matched controls to adjust for any known confounders and additional time points (baseline, 48 hours, 2 weeks, and 6 weeks). In addition, any covariate at the individual level that is simultaneously unbalanced and associated with the outcome will be included in the model. Covariates of interest include demographic variables (e.g., ethnicity, Illness Day at diagnosis, response to IVIG therapy). Permutation tests may be implemented to verify that valid p-values will be obtained even if model assumptions are not correct. Note that the mixed model seamlessly accommodates different times of measurement (e.g. 2-week and 6-week time points) as well as missed measurements and data from subjects who are lost to follow-up. A corresponding Generalized Estimating Equations (GEE) model will be used as the sensitivity analysis method. An analogous secondary model including all subjects in this study will also be considered to examine the dose versus activity relationship. In this model, dosage will be included as a covariate to examine any dosage trend in activity.

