The above approach will be repeated for the other markers. That is, multi-level mixed effects regression models analogous to the above methodology will be applied for other markers: Levels of high sensitivity (hs) CRP, alpha-1 antitrypsin, TNFaR1 and R2, IFNg, IL-1 RAP, IL-1R1 and R2, MMP9, caspase-1, IL-6R, IL-18RAP, IL-12, IL-2, TGFb and IL-10.

Measures of transcript abundance will also be analyzed via microarray analysis. Data will be preprocessed first and then microarray analysis procedures will be used to measure abundance. The R software (version 3.0.2) and Bioconductor package in R will be used for the analysis. For coronary outcomes as assessed by echocardiography, we will compare the delta Z scores (baseline minus 2weeks and 6-weeks) between anakinra subjects and matched controls. A GEE model will be used as the sensitivity analysis method. Since this is a safety and early efficacy study, no adjustments for multiple comparisons will be made for biomarker analyses. P-values less than 0.05 will be considered statistically significant. All statistical analyses will be performed in R version 3.2.0 (www.rproject.org/). Similarly, analyses will be repeated on all subjects to characterize any dose-activity relationship, adjusting for dosage as a covariate in the model.

To determine the "best" or "set of best" markers that have the greatest improvement from baseline in anakinra-treated patients, ROC and AUROC analysis will be considered. In the event that there is

high multi-collinearity amongst the markers, we will adopt the "glmpath" approach, which is based on Least Angle Regression (LARS) methods to select the best biomarkers (Park 2007).

Missing data assumptions: The proposed mixed-effects regression model is consistent under the assumption that the outcome data are "missing at random" (MAR), that is, mixed models with a random effect assume only that the probability that an outcome is missing depends on observed outcomes. GEE models, which are proposed as a sensitivity analysis, assume that the outcome data are "missing completely at random", that is, that the probability that an outcome is missing does not depend on any previous, present or succeeding value of the outcome. This will enable us to assess the impact of the missing data mechanism on statistical inferences drawn from these models.

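### Phase I/IIa week-6 marker blood is drawn only from subjects still on drug, but the marker analyses use week 6 without that limit, and the planned GEE comparison cannot show the resulting bias

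*Combined protocol and SAP*

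**What the plan says.** **Collection.** Section 11E1 takes RNA, plasma, serum and heparinized whole blood at baseline, "48 hours and 2 and up to 6 weeks (if still on study drug". Section 11D1 (clinical data, item e) lists WBC, hsCRP, ESR, fibrinogen and alpha-1-antitrypsin, with the later draws at "2 weeks and 6 weeks (if still on study drug) after drug administration".

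**Who is on drug.** Under Section 12B1 everyone is treated for 2 weeks. Those with a 2-week LAD or RCA Z-score of at least 2.0 "will receive an additional 4 weeks of therapy to complete a total course of 6 weeks". A dose-limiting toxicity (DLT) also ends treatment (Section 12F1). Follow-up does not end with treatment: "All subjects will remain on study for the full 6 weeks whether or not they are receiving anakinra".

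**Use.** Specific Aim 2 (Section 9A): "Blood will be tested pre-drug administration, 48 hours after initiation of therapy and at 2 weeks and 6 weeks". Section 17 separates cells "at three time points (pre-treatment, 2 weeks, and 6 weeks post-treatment". Section 19B1 fits mixed models "to adjust for any known confounders and additional time points (baseline, 48 hours, 2 weeks, and 6 weeks". None of these repeats the on-drug limit. Sections 18A and 19B1 do not say whether the historical controls have week-6 samples.

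**Missing data.** Section 19B1 takes the mixed model as valid under MAR and a GEE as valid under MCAR, and says of using both: "This will enable us to assess the impact of the missing data mechanism on statistical inferences drawn from these models".

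**The concern.** The gap at week 6 is not sporadic. It is fixed in advance by a rule based on 2-week coronary response. Matching controls on baseline Z does not remove selection on 2-week Z, and the covariates named in Section 19B1 include neither 2-week Z nor drug status. That section speaks of missed measurements and loss to follow-up, not of this planned non-collection, and it does not define what week-6 effect is being estimated.

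Apart from deviations, every child below Z 2.0 at week 2 is off drug, and none of them gives a week-6 marker. The trial therefore observes nothing about markers four weeks after stopping. A week-6 result from the remaining subset could be read as the effect in all treated children when it is not, and the planned sensitivity analysis would not warn the reader.

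**Working it through.** **1. The plan's own figure.** Section 15A: 18 pairs, two-sided paired t-test, alpha 0.05, differences 2.2 with SD 3.2 (2.2/3.2 = 0.6875) and 5.6 with SD 8 (5.6/8 = 0.70). Noncentral t with 17 degrees of freedom gives power 78.5% and 79.9%, close to the stated 80%. This works only if the stated SD is that of the paired difference; an independent two-sample calculation (normal approximation) gives 54% and 56%.

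**2. Inputs that the documents do not give (assumed).**
- Share on drug after week 2, p: one third to two thirds, and separately 80% to 90%.
- Correlation of 2-week Z with the week-6 marker, r: 0.3 to 0.5.
- Correlation of baseline with 2-week Z, q: 0.5 to 0.8.
- Share of the on-drug effect that remains off drug, f: 0 to 1.

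**3. Selection bias.** Let Z be standard normal and let c be the cut that leaves a share p above it. Treated subjects with week-6 data have a mean marker shift of r × φ(c)/p. Their controls, matched on baseline Z only, share r × q² × φ(c)/p of it. The bias in the contrast is

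b = r(1 − q²) × φ(c)/p.

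| p | φ(c)/p | b at r = 0.3, q = 0.8 | b at r = 0.5, q = 0.5 |
|---|---|---|---|
| 1/3 | 1.091 | 0.118 | 0.409 |
| 1/2 | 0.798 | 0.086 | 0.299 |
| 2/3 | 0.545 | 0.059 | 0.205 |
| 0.8 | 0.350 | 0.038 | 0.131 |
| 0.9 | 0.195 | 0.021 | 0.073 |

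So b is 0.06 to 0.41 marker SD for one third to two thirds on drug, and 0.02 to 0.13 for 80% to 90%.

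**4. Direction.** With on-drug reduction E, the observed contrast is −E + b whatever happens off drug. The effect in all treated subjects is −E[p + (1 − p)f]. The two are equal at f = 1 − b/[E(1 − p)]. Above that f the observed contrast understates the effect; below it, it overstates.

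Example with p = 1/2, r = 0.3, q = 0.8 and E = 0.70 marker SD: observed −0.70 + 0.086 = −0.614. The all-subjects effect is −0.70 if f = 1 (understated by 0.09) and −0.35 if f = 0 (overstated by 0.26).

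For p from one third to two thirds, the break-even f depends on how the SD in Section 15A is read:
- As marker SD, E = 0.70: lowest 1 − 0.409/(0.70 × 0.667) = 0.12; highest 1 − 0.086/(0.70 × 0.5) = 0.75.
- As paired-difference SD, the reading that reproduces 80%: if pairs correlate only through Z, the within-pair correlation is (rq)² and the difference has SD √(2[1 − (rq)²]). At r = q = 0.5 this is 1.369, so E = 0.958 and f = 1 − 0.409/(0.958 × 0.667) = 0.36. At r = 0.3, q = 0.8 it is 1.373, so E = 0.961 and f = 1 − 0.086/(0.961 × 0.5) = 0.82.

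**5. What the GEE comparison shows.** Simulated treated-arm means on the IL-1RAP scale (SD 3.2, design difference 2.2), with half on drug. The mixed model is represented by regression of week 6 on week 2, the GEE by an independence working correlation; the plan names no working correlation.

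| r | Rebound off drug | Bias, mixed | Bias, GEE | Gap |
|---|---|---|---|---|
| 0.3 | 0 | +0.55 | +0.76 | +0.22 |
| 0.3 | 3.2 | −1.05 | −0.83 | +0.22 |
| 0 | 1 | −0.50 | −0.50 | 0.00 |

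The gap is the same while the bias changes sign, and it vanishes while both models are biased. The reason is general: off-drug week-6 values never enter either fit.

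**6. Precision, as illustration only.** If half of 18 subjects gave week-6 blood, nine 1:1 pairs would have 44% to 46% power for the Section 15A effects. Section 15A names no time point and Section 18A plans 1:2 matching, so this is not the power of a stated analysis.

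**The case against.** Sections 11D1 and 11E1 are the operative sampling rules, and the other sections may simply list nominal visits. Section 11F likewise lists a 6-week trough sample without an on-drug limit, although a trough presupposes dosing. This has force: a short clarification would settle the textual mismatch. It would not say what the week-6 contrast estimates.

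Section 19B1 labels MAR and MCAR correctly and does not claim to test MAR. That also stands. A gap between the models may hint that MCAR fails. The sentence on assessing the missing-data mechanism still promises more than the comparison can give.

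The share on drug could be high, since entry requires Z of at least 2.5 and treatment stops only if both vessels are below 2.0. The bias is then small, as the 80% to 90% rows show. If controls have no week-6 samples, there is no week-6 contrast to bias. Limiting blood draws in children who may be as young as 28 days may also be deliberate.

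A reader might infer that the bias runs toward no effect. The documents do not support that: it holds only if enough of the effect persists off drug, about which they say nothing. Nor would imputing from 2-week Z recover the effect in all treated subjects; it carries on-drug behaviour over to children who are off drug.

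**Conclusion.** The concern holds as a gap between collection and analysis, and it should be fixed. The text is clear: week-6 marker blood depends on drug status, the analyses do not, and no matching limit is set for controls. If controls have week-6 data, the contrast does not estimate the effect in all treated subjects.

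The size rests wholly on assumed inputs: about 0.06 to 0.41 marker SD of selection bias with one third to two thirds on drug, and 0.02 to 0.13 with 80% to 90%. The sign is unknown. For one third to two thirds on drug it reverses at 12% to 75% retention of effect off drug on the marker-SD reading, or 36% to 82% on the paired-difference reading.

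The reach is limited. Markers are secondary outcomes (Section 7G1), and the 48-hour and 2-week markers and the 6-week echo are not touched. A reader might also infer that the combination pilot's sampling section (11E2) contradicts its assay times in Section 18B. It does not, because it only provides for conditional collection; the mismatch there is between Sections 19B2 and 18B.

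**What to change.** 1. Reconcile Sections 11D1 and 11E1 with Aim 2 and Sections 17 and 19B1. Preferably take the week-6 marker sample from all subjects at the existing week-6 visit, record drug status at the draw, and state in Section 19B1 that the week-6 estimand is regardless of drug status. The cost is one extra blood draw in children who stopped drug at week 2.
2. If the limit stays, or for samples already missed, label week-6 marker results as describing only subjects still on drug, restrict matched controls to 2-week Z of 2.0 or more, and do not present the results as the effect in all treated subjects. Because 2-week Z is itself measured after treatment starts, the result remains descriptive. Either way, state whether controls have week-6 samples.
3. Label any imputation from 2-week Z as estimating the effect had all stayed on drug.
4. In Section 19B1, replace the claim for the GEE with a delta-adjusted (MNAR) sensitivity analysis of week-6 markers, with deltas from zero to full loss of the on-drug effect, on a stated SD scale.
5. Separately, reconcile Sections 12C1, 12D, 12E and 12F1 with Section 11D1 on the 6-week WBC in subjects off drug. WBC is a DLT criterion, and this review takes no view on which rule is right.
6. For the combination pilot, reconcile the week-6 time point in Section 19B2 with Section 18B, which stops at 2 weeks.

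Items 2 to 6 need wording, or analysis of data already planned.
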